7.3. Safety Parameters

Safety parameters will be assessed as described in the [Schedule of Activities](#) and below.

A medical history and physical examination will be performed on all subjects, to establish a baseline. Significant medical history and observations from the physical examination will be documented in the CRF.

The safety parameters include e-diary reports of local reactions and systemic events that occur in the 14 days after investigational product administration at each vaccination visit. These prospectively collected occurrences of local reactions and systemic events are graded as described in [Section 7.3.1](#).

In the Primary Study Cohort - Stage 1, the first 4 subjects vaccinated in the study must be observed by blinded site staff for any acute reactions for at least 4 hours after vaccination. Vaccination of subjects will be limited to a maximum of 6 subjects per day during the first week of enrollment (up to 30 vaccinated subjects in total) to maintain safety oversight.

For subjects enrolled, thereafter, irrespective of study cohort, blinded site staff must observe subjects for any acute reactions for at least 30 minutes after investigational product administration. Acute reactions after investigational product administration will be assessed and documented.

In addition, AEs, medically attended AEs (MAEs), AEs of specific interest, and SAEs are collected, recorded, and reported as defined in [Section 8](#). An MAE is defined as a nonserious AE that results in an evaluation at a medical facility.

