8.1.4. Time Period for Collecting AE/SAE Information

The time period for actively eliciting and collecting AEs and SAEs (“active collection period”) for each subject begins from the time the subject provides informed consent, which is obtained before the subject’s participation in the study (ie, before undergoing any study-related procedure and/or receiving investigational product), as follows:

- SAEs: From informed consent until study completion.
- AEs:
 - Primary Study Cohort - Stage 1: Informed consent until Visit 2 (1 month after Vaccination 1). Thereafter MAEs will be collected.
 - Primary Study Cohort - Stage 2: Visit 5 until Visit 6 (1 month after Vaccination 2). Thereafter MAEs will be collected.
 - RSV Vaccine Month-0, Month-2 Cohort: Informed consent until Visit 4 (1 month after Vaccination 2). Thereafter MAEs will be collected.
- Occurrences of AEs of specific interest (refer to [Table 10](#)) will be recorded from administration of the investigational product until the subject completes the study, regardless of causality.

- Any AE occurring up to 48 hours after the blood draws at all study visits must be recorded and reported in the CRF.
- All AEs should be followed for resolution throughout the study. Stop dates are to be recorded in the CRF and source documents.

For subjects who are screen failures, the active collection period ends when screen failure status is determined.

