8.4.2. Adverse Events of Specific Interest

AEs of specific interest for safety monitoring include the occurrence of autoimmune disorders listed in Table 10. These events will be documented as AEs on the CRF and reported as SAEs if the event meets the seriousness criteria ([Section 8.2.3](#)). **Notification of AEs of specific interest to the Pfizer clinical team and completion of the AE CRF page should be done within 24 hours of investigator awareness.**

Table 10. Autoimmune Diseases/Disorders

Gastrointestinal disorders	
 • Celiac disease • Crohn disease • Ulcerative colitis • Ulcerative proctitis
Liver disorders	
 • Autoimmune cholangitis • Autoimmune hepatitis • Primary biliary cirrhosis • Primary sclerosing cholangitis
Metabolic disorders	
 • Addison disease • Autoimmune thyroiditis (including Hashimoto thyroiditis) • Diabetes mellitus type 1 • Graves or Basedow disease

Table 10. Autoimmune Diseases/Disorders

Musculoskeletal disorders	
 • Antisynthetase syndrome • Dermatomyositis • Juvenile chronic arthritis (including Still disease) • Mixed connective tissue disorder • Polymyalgia rheumatica • Polymyositis • Psoriatic arthropathy • Relapsing polychondritis • Rheumatoid arthritis • Scleroderma, including diffuse systemic form and CREST syndrome • Spondyloarthritis, including ankylosing spondylitis, reactive arthritis (Reiter syndrome), and undifferentiated spondyloarthritis • Systemic lupus erythematosus • Systemic sclerosis
Neuroinflammatory disorders	
 • Acute disseminated encephalomyelitis, including site-specific variants, eg, noninfectious encephalitis, encephalomyelitis, myelitis, radiculomyelitis • Cranial nerve disorders, including paralyses/paresis (eg, Bell palsy) • Guillain-Barré syndrome, including Miller Fisher syndrome and other variants • Immune-mediated peripheral neuropathies and plexopathies, including chronic inflammatory demyelinating polyneuropathy, multifocal motor neuropathy, and polyneuropathies associated with monoclonal gammopathy • Multiple sclerosis • Narcolepsy • Optic neuritis • Transverse myelitis • Myasthenia gravis, including Eaton-Lambert syndrome

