9.3. Safety Analysis

Safety and tolerability results will be summarized by vaccine group and by study cohort.

All subjects receiving at least 1 dose of the investigational products will be included in the safety population. For the safety analyses, subjects will be analyzed according to the investigational product received.

The safety endpoints are primary endpoints in the study and their analyses are based on the safety population.

The safety analyses are descriptive evaluations of local reactions, systemic events, AEs, MAEs, AEs of specific interest, and SAEs. AEs will be categorized according to the Medical Dictionary for Regulatory Activities (MedDRA).

Descriptive summary statistics (eg, counts and percentages) will be provided for AEs and e-diary events, with 2-sided 95% exact CIs as appropriate.

The 3-tier approach will be used for the summary of AEs. Detailed definitions for each tier will be described in the SAP.

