3.1.4. Adverse Events

AE reporting will be based on the specific reporting period. Standard algorithms for handling missing AE dates and missing AE severity will be applied as described in the Pfizer Vaccine data standard rules.

As this is a Phase 1/2 study, with limited sample size included in each vaccine group, the value of applying the 3-tier approach is limited. Therefore, because of a small number of

subjects in each dose/formulation group, safety assessment may be best carried out using descriptive statistics.

For AEs within 1 month after each vaccination, the interval calculation will be based on the study visit. For example, for the Primary Study Cohort - Stage 1, AEs within 1 month after Vaccination 1 will include any AE that occurred from the day of Vaccination 1 until the day before the 1-month post-Vaccination 1 visit (Visit 2). In general, this will be derived for each vaccination:

- Primary Study Cohort - Stage 1: AEs within 1 month after Vaccination 1.
- Primary Study Cohort - Stage 2: AEs within 1 month after Vaccination 2.
- RSV Vaccine Month-0, Month-2 Cohort – AEs within 1 month after Vaccination 1.
- RSV Vaccine Month-0, Month-2 Cohort – AEs within 1 month after Vaccination 2.

The following derivations/summaries will be included for each of the above:

1. Proportions of subjects reporting AEs during this interval summarized for each system organ class (SOC) and preferred term (PT) (and “any event”), separately.
2. Proportion of subjects reporting any AE during this interval.
3. Proportion of subjects reporting any MAE during this interval.
4. Proportion of subjects reporting any SAE during this interval.
5. Proportion of subjects reporting any related AE during this interval.
6. Proportion of subjects reporting any severe AE during this interval.
7. Proportion of subjects reporting any intermediate AE. Intermediate AE is defined as an AE reported within the first 30 minutes after vaccination.
8. Proportion of subjects reporting any AE leading to withdrawal during this interval.
9. Proportion of subjects reported any AE of specific interest (Refer to Section 8.4.2 of the protocol for details on the diseases/disorders included in this category).

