3.1.5. Medically Attended AEs and Serious AEs

Proportions of subjects reporting SAEs and MAEs will be summarized for each SOC and PT (and “any event”), separately, for the following intervals:

- Primary Study Cohort - Stage 1: MAEs (or SAEs) through 12 months after Vaccination 1.

CCI

PFIZER CONFIDENTIAL

- Primary Study Cohort - Stage 2: MAEs (or SAEs) through 12 months after Vaccination 2.
- RSV Vaccine Month-0, Month-2 Cohort: MAEs (or SAEs) through 12 months after Vaccination 2.

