6.1.4.2. Additional Summary for Assessing Adverse Events

To support the assessment of AEs, similar endpoints as above will be summarized for the Primary Study Cohort - Stage 2 within 1 month after Vaccination 2; as well as for the RSV Vaccine Month-0, Month-2 Cohort within 1 month after each vaccination and from Vaccination 1 through 1 month after Vaccination 2.

To support the assessment of AEs, additional endpoints by category (related AE, severe AE, SAE, MAE, immediate AE, AE leading to withdrawal, AE of specific interest), as defined in [Section 3.1.4](#), will be summarized with all analysis time points (within 1 month after Vaccination 1 and within 1 month after Vaccination 2), analysis populations (Primary Study Cohort - Stage 1, Primary Study Cohort - Stage 2, and RSV Vaccine Month-0, Month-2 Cohort), analysis methodology, and appropriate reporting results.

For each specific AE category (related AE, severe AE, SAE, MAE, immediate AE, AE leading to withdrawal), if the total number of subjects is >10% of the study population, the analysis summary by SOC and PT will also be provided for that category. Otherwise, only listings of these AEs will be provided by SOC, PT, and category designation (SAE, MAE, immediate AE, etc.).

If any nonserious AEs are reported to occur before vaccination or more than 1 month after vaccination (outside of the protocol-specified reporting window), they will not be summarized, but will be included in the AE listings.

Figures: Bar charts with the proportions of subjects reporting each AE category after vaccination will be plotted for each vaccine group.

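### AEs of specific interest are collected to study completion, but the SAP plans no count by vaccine group of subjects with any such event beyond 1 month after a vaccination

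*SAP*

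**What the plan says.** **Collection.** Protocol 8.4.2 defines the category: "AEs of specific interest for safety monitoring include the occurrence of autoimmune disorders listed in Table 10". Under Protocol 8.1.4 these events "will be recorded from administration of the investigational product until the subject completes the study, regardless of causality". The schedules of activities (Protocol Tables 1 to 3) include them at every visit.

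**Analysis promised in the protocol.** Section 9.3 states: "The safety analyses are descriptive evaluations of local reactions, systemic events, AEs, MAEs, AEs of specific interest, and SAEs". It sets no 1-month limit on AESIs.

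**Analysis planned in the SAP.**

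- SAP 3.1.4 sets four intervals, each within 1 month after a vaccination. Its Stage 1 example runs "from the day of Vaccination 1 until the day before the 1-month" visit. A list of nine derivations is then applied to each interval, and the ninth is "Proportion of subjects reported any AE of specific interest".
- SAP 6.1.4.2 names the AESI category with the others and says they "will be summarized with all analysis time points (within 1 month after Vaccination 1 and within 1 month after Vaccination 2"). It then sends nonserious AEs later than 1 month after vaccination to listings only, on the ground that they fall outside the protocol's reporting window.
- SAP 3.1.5 supplies the long-term summaries: "Proportions of subjects reporting SAEs and MAEs will be summarized for each SOC and PT", through 12 months. Sections 6.1.5 and 6.1.6 carry this out for SAEs and MAEs and mention no AESIs.
- SAP 6.6 says that every safety summary is in Section 6.1.

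**The concern.** The protocol treats AESIs as a category of their own and follows them to the end of the study. The SAP gives that category a summary that stops at 1 month. It also describes the later period as outside the protocol's reporting window, which is not so for AESIs under Protocol 8.1.4. SAP 2.2, which sets out the collection periods, covers SAEs, AEs and MAEs but not AESIs, so the longer period may simply have been overlooked.

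The practical cost is a missing count. Protocol 7.3 says: "An MAE is defined as a nonserious AE that results in an evaluation at a medical facility". A late AESI that is serious therefore goes to the SAE table and one that is medically attended but nonserious goes to the MAE table. One that is neither would be listed only. The two tables are organized by system organ class and preferred term and do not mark AESIs. A reader wanting the number of subjects with any AESI would have to match Table 10 against preferred terms in both tables and the listings, then remove subjects counted twice. The only pooled AESI proportion with a confidence interval would be the 1-month one, and it could be taken for the study's AESI rate.

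**Working it through.** The plan attaches no figure to AESIs. The nearest is the example for Protocol Table 11 (31 subjects, true rate 5%): 1 − 0.95^31 = 0.796, which reproduces the stated 80%. All 20 cells agree to within 0.02, and none is affected by this point.

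**1. Summary window against collection window**

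| Event type | Collected until (Protocol 8.1.4) | Summarized until (SAP 3.1.4, 3.1.5, 6.1.4–6.1.6) |
|---|---|---|
| SAE | Study completion | 12 months after the relevant vaccination |
| MAE | Final visit | 12 months after the relevant vaccination |
| AESI | Study completion | Day before the 1-month visit |

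AESI is the only one of the three whose category summary stops short of its collection period.

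**2. Share of follow-up covered by the 1-month AESI row**

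Inputs are the visit windows in Protocol Tables 1 to 3. The 1-month visit is 28–35 days after vaccination, so a window ending the day before it spans 28–35 days. Stage 1 ends 300–400 days after Visit 1. Stage 2 ends 350–378 days after Visit 5. In the Month-0, Month-2 Cohort, Vaccination 2 is 54–66 days after Visit 1 and the last visit is 350–378 days after Vaccination 2.

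Share = days in the summary window ÷ days of follow-up.

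| Cohort | Lowest | Highest |
|---|---|---|
| Stage 1 | 28/400 = 7.0% | 35/300 = 11.7% |
| Stage 2 | 28/378 = 7.4% | 35/350 = 10.0% |
| Month-0, Month-2, two 1-month windows | (28+28)/(66+378) = 56/444 = 12.6% | (35+35)/(54+350) = 70/404 = 17.3% |
| Month-0, Month-2, Vaccination 1 through 1 month after Vaccination 2 | (54+28)/(54+378) = 82/432 = 19.0% | (66+35)/(66+350) = 101/416 = 24.3% |

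The last row is the widest reading. SAP 6.1.4.2 gives that interval for AEs overall in this cohort, but not in the sentence that names AESIs. Across all rows the uncovered share runs from 100 − 24.3 = 75.7% to 100 − 7.0 = 93.0%.

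**3. What one late event would do to the row**

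Assume one AESI after the 1-month visit and none before it, in a group of 31 (the approximate group size in Protocol Table 4). Clopper-Pearson 95% limits:

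- 1-month row, 0/31: the upper limit is 1 − 0.025^(1/31) = 11.2%, so 0% (0–11.2%).
- Full-period row, 1/31 = 3.2%: the lower limit is 1 − 0.975^(1/31) = 0.1% and the upper limit is 16.7%.

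**4. Size of the matching task**

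Table 10 entries by group, in table order: 4 + 4 + 4 + 13 + 9 + 9 + 2 + 13 = 58 entries in 8 groups.

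**The case against.** Six points can be made for the plan.

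- **The ninth item in SAP 3.1.4 has no interval wording of its own**, unlike most of the items before it, so a longer window may have been meant. That is a fair reading of the item alone. But its lead-in applies it to each of the four 1-month intervals, and 6.1.4.2 states the two time points outright. If a longer window was intended, the text still needs correcting.
- **The listing-only rule may not reach AESIs.** It is framed around events outside the protocol's reporting window, and late AESIs are inside it. Nor can it cover every late nonserious event, since MAEs are nonserious and are tabulated to 12 months. This stands in part: the exemption asked for is a clarification. It does not supply the missing row.
- **Most late AESIs would be tabulated anyway.** Table 10 consists of diagnoses, and a new one would usually involve a medical evaluation. Sections 6.1.5 and 6.1.6 would then give its preferred term a proportion and interval by vaccine group. This stands, and it is the main reason the point is minor. The event in step 3 would show as 1/31 in such a row.
- **With few events, a reader can check them against Table 10** rather than search all 58 entries. True, though the count would still be assembled by hand. The category labels that 6.1.4.2 gives for its listings do not name AESI.
- **Table shells are prepared separately** (SAP Section 2) and might include such a row. That cannot be excluded, but SAP 6.6 places all safety summaries in Section 6.1, where none is described.
- **No endpoint is breached.** Correct: AESI is not among the endpoints in Protocol Section 2, and Protocol 9.3 sets no interval.

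**Conclusion.** The concern holds, as a minor one. As written, the SAP gives a proportion with any AESI by vaccine group only within 1 month after each vaccination, while the protocol collects these events to study completion. The planned row leaves out roughly 76–93% of the collection period, depending on cohort and reading. That range is calendar time under the protocol's visit windows. It says nothing about when AESIs would occur, and the documents give no expected AESI rate.

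Late AESIs are not lost, and the primary endpoints are unaffected. What is missing is a direct count over the full period for a category that the protocol names as a safety analysis, in a study whose interim results will inform the choice of dose, formulation and schedule (Protocol 9.4).

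**What to change.** In SAP 3.1.5 and 6.1.5, add one any-AESI row per cohort, with n/N and Clopper-Pearson 95% CI by vaccine group in that cohort's safety population:

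- Stage 1: Visit 1 through Visit 5.
- Stage 2: Visit 5 through Visit 9.
- Month-0, Month-2 Cohort: Visit 1 through Visit 6.

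Add a listing of AESIs by preferred term, and keep the 1-month row as a sub-interval. In 6.1.4.2, state that the listing-only rule for late nonserious AEs does not apply to AESIs.

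The cost is SAP wording, one table row per cohort and a listing. No new data are needed, and the primary analysis does not change.

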
RSV Vaccine Month-0, Month-2 Cohort
 
To describe the safety and tolerability of the first and second dose of an adjuvanted RSV vaccine administered 2 months apart.
 
To describe the immune responses elicited by the first and second dose of adjuvanted RSV vaccine administered 2 months apart.
	
RSV Vaccine Month-0, Month-2 Cohort
 
 • Local reactions within 14 days after Vaccinations 1 and 2. • Systemic events within 14 days after Vaccinations 1 and 2. • AEs within 1 month after Vaccinations 1 and 2. • AEs from Vaccination 1 through 1 month after Vaccination 2. • Medically attended AEs and SAEs through 12 months after Vaccination 2. • RSV A– and RSV B–neutralizing antibody titers measured at scheduled timepoints before and after each vaccination scheduled. • Plasmablast frequencies and T-cell phenotype and functional analysis before each vaccination and 1 week after Vaccinations 1 and 2 (PBMC subjects). • Memory B-cell and T-cell frequencies and their functional analysis before each vaccination, and 1 and 6 months after Vaccinations 1 and 2. • IgG titers against prefusion F at scheduled timepoints before and after each vaccination. • IgG titers to nonvaccine RSV antigens at scheduled timepoints before and after each vaccination.

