- The investigator or appropriately qualified designee reviews the e-diary data online following vaccination to evaluate subject compliance and as part of the ongoing safety review. Daily review is optimal during the active diary period.

6.3.2. RSV Vaccine Month-0, Month-2 Cohort, Visit 2A: 1-Week Follow-up Visit (6 to 8 Days After Visit 1) (*applies to subjects consenting to PBMC collection at PBMC collection sites only*)

- Review the subject's e-diary data.
- Record nonstudy vaccinations as described in [Section 5.8.4](#).
- Confirm understanding of and compliance with protocol requirements for contraception (male subjects only).
- Collect a blood sample of approximately 50 mL for cellular assays.
- Record AEs as described in [Section 8](#).
- Ask the subject to contact the site staff or investigator if a medically attended event (eg, doctor's visit, emergency room visit) or hospitalization occurs.
- Schedule an appointment for the subject to return for the next study visit.

- Complete the source documents.
- The investigator or an authorized designee completes the CRFs.

6.3.3. RSV Vaccine Month-0, Month-2 Cohort, Visit 2: 1-Month Follow-up Visit (28 to 35 Days After Visit 1) (*applies to all subjects*)

- Review the subject's e-diary data and collect the e-diary. Collect stop dates of any e-diary events ongoing on the last day that the e-diary was completed and record stop dates in the CRF if required.
- Record nonstudy vaccinations as described in [Section 5.8.4](#).
- Confirm understanding of and compliance with protocol requirements for contraception (male subjects only).
- Collect a blood sample of approximately 25 mL for antibody assessment.
- Collect a blood sample of approximately 50 mL for cellular assays (from consenting PBMC subjects at PBMC collection sites only).
- Record AEs as described in [Section 8](#).
- Complete the source documents.
- The investigator or an authorized designee completes the CRFs.
- Ask the subject to contact the site staff or investigator if a medically attended event (eg, doctor's visit, emergency room visit) or hospitalization occurs.

6.3.4. RSV Vaccine Month-0, Month-2 Cohort, Visit 3: Vaccination 2 Visit (54 to 66 Days After Visit 1) (*applies to all subjects*)

- Record nonstudy vaccinations as described in [Section 5.8.4](#).
- Ensure that the subject meets none of the temporary delay criteria as described in [Section 4.3](#).

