- Remind the subject to bring the completed e-diary to the next visit.

- Complete the source documents.
- The investigator or an authorized designee completes the CRFs and an unblinded dispenser/administrator updates the investigational product accountability records.
- The investigator or appropriately qualified designee reviews the e-diary data online following vaccination to evaluate subject compliance and as part of the ongoing safety review. Daily review is optimal during the active diary period.

6.3.5. RSV Vaccine Month-0, Month-2 Cohort, Visit 4A^a: 1-Week Post-Vaccination 2 Follow-up Visit (6 to 8 Days After Visit 3) (*applies to subjects consenting to PBMC collection at PBMC collection sites only*)

- Review the subject's e-diary data.
- Record nonstudy vaccinations as described in [Section 5.8.4](#).
- Confirm understanding of and compliance with protocol requirements for contraception (male subjects only).
- Collect a blood sample of approximately 50 mL for cellular assays.
- Record AEs as described in [Section 8](#).
- Ask the subject to contact the site staff or investigator if a medically attended event (eg, doctor's visit, emergency room visit) or hospitalization occurs.
- Schedule an appointment for the subject to return for the next study visit.
- Remind the subject to bring the completed e-diary to the next visit.
- Complete the source documents.
- The investigator or an authorized designee completes the CRFs.

6.3.6. RSV Vaccine Month-0, Month-2 Cohort, Visit 4: 1-Month Post-Vaccination 2 Follow-up Visit (28 to 35 Days After Visit 3) (*applies to all subjects*)

- Review the subject's e-diary data and collect the e-diary. Collect stop dates of any e-diary events ongoing on the last day that the e-diary was completed and record stop dates in the CRF if required.
- Record nonstudy vaccinations as described in [Section 5.8.4](#).
- Confirm understanding of and compliance with protocol requirements for contraception (male subjects only).
- Collect a blood sample of approximately 25 mL for antibody assessment.

- Collect a blood sample of approximately 50 mL for cellular assays (from consenting PBMC subjects at PBMC collection sites only).
- Record AEs as described in [Section 8](#).
- Complete the source documents.
- The investigator or an authorized designee completes the CRFs.
- Ask the subject to contact the site staff or investigator if a medically attended event (eg, doctor's visit, emergency room visit) or hospitalization occurs.

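### In the exploratory Month-0, Month-2 Cohort, the related, severe and withdrawal AE counts have no interval covering the weeks between the 1-month visit and the second dose

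*SAP*

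**What the plan says.** **Collection.** Protocol 8.1.4 sets the AE period for this cohort as "RSV Vaccine Month-0, Month-2 Cohort: Informed consent until Visit 4 (1 month after Vaccination 2"), with only medically attended AEs collected afterwards. There is no pause between the two doses. Protocol 2 lists "AEs from Vaccination 1 through 1 month after Vaccination 2" among the cohort's exploratory endpoints, and SAP 3.3 repeats it.

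**Intervals.** SAP 3.1.4 bases the 1-month interval on visits. Its Stage 1 example counts AEs from the day of vaccination "until the day before the 1-month post-Vaccination 1 visit (Visit 2"), and the text carries this over to each vaccination. For the two-dose cohort it lists two intervals, one after each dose. The category proportions are then attached to the listed intervals. The continuous interval is not on that list.

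**Summaries.** The first paragraph of SAP 6.1.4.2 gives this cohort the overall AE, SOC and PT summary for each 1-month interval and also for the continuous interval. The second paragraph, on categories, says they "will be summarized with all analysis time points (within 1 month after Vaccination 1 and within 1 month after Vaccination 2") and does not add the continuous interval.

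**Closing rule.** SAP 6.1.4.2 then says: "If any nonserious AEs are reported to occur before vaccination or more than 1 month after vaccination", these events are listed and not summarized. A parenthesis describes them as lying outside the protocol's reporting window.

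**The concern.** In a single-dose cohort, the 1-month interval and the AE collection period end at about the same visit, so nothing falls between them. In the two-dose cohort they separate. Collection runs on through the second month, but the category counts stop at Visit 2 and restart at Vaccination 2. A related or severe nonserious AE with onset on, say, Day 40 is collected and assessed for causality and severity, yet no category count includes it.

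Related and severe AEs are a standard readout of tolerability. This cohort exists to describe the tolerability of two doses given 2 months apart, and Protocol 9.4 and SAP 7.2 say the interim results will help select the dosing schedule. The paragraph just before the category text includes the continuous interval, and the SAP gives no reason for leaving it out of the categories. It reads as an omission and not as a decision.

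**Working it through.** **The plan's own figure.** The documents give no figure for the uncovered time. The only related number is Protocol Table 11, the chance of seeing at least one AE, which is 1 − (1 − p)^n. With p = 0.05 and n = 31 this is 1 − 0.95^31 = 0.796, matching the stated 0.80. All 20 cells of the table reproduce.

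**Inputs** (Protocol 6.3.3, 6.3.4 and 6.3.6, and Protocol Table 3):

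- "Visit 2: 1-Month Follow-up Visit (28 to 35 Days After Visit 1"): call the day v2, 28 to 35.
- "Visit 3: Vaccination 2 Visit (54 to 66 Days After Visit 1"): call the day v3, 54 to 66.
- Visit 4, "28 to 35 Days After Visit 3": call the offset v4, 28 to 35.

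**Formulas.** The first category interval ends the day before Visit 2 and the second starts on the day of Vaccination 2. The uncovered days run from Visit 2 to the day before Vaccination 2.

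- Gap = v3 − v2.
- Window from Vaccination 1 to the day before Visit 4 = v3 + v4.
- Uncovered share f = (v3 − v2) / (v3 + v4).

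**Results.**

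| Quantity | Calculation | Result |
|---|---|---|
| Shortest gap | 54 − 35 | 19 days |
| Longest gap | 66 − 28 | 38 days |
| Shortest window | 54 + 28 | 82 days |
| Longest window | 66 + 35 | 101 days |
| Share at window midpoints | (60 − 31.5) / (60 + 31.5) = 28.5 / 91.5 | 31.1% |
| Smallest share (v2 = 35, v3 = 54, v4 = 35) | 19 / 89 | 21.3% |
| Largest share (v2 = 28, v3 = 66, v4 = 28) | 38 / 94 | 40.4% |

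The mean share over all in-window combinations of visit days is also 31.1%. If the category counts used the continuous interval, the uncovered time would be 0 days.

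**Illustration only.** The documents give no AE rate for the gap. Assume that 5% of subjects would have a given category of event over the whole window, at constant hazard. The chance that a 31-subject arm shows at least one in the category counts is then 1 − 0.95^(31(1 − f)):

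- full coverage (f = 0): 0.80;
- f = 31.1%: 0.67;
- f = 21.3%: 0.71;
- f = 40.4%: 0.61.

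**The case against.** The strongest reply is that little is missing. Every AE in the gap is counted, by vaccine group, in the any-AE, SOC and PT summary over the continuous interval. The protocol endpoint names that interval but does not ask for it by category, so the endpoint is delivered. SAEs are summarized through 14 months after Vaccination 1 (SAP 6.1.5.2), and MAEs are handled the same way (SAP 6.1.6). All AEs are listed. The 14-day e-diary data after each dose are unaffected. All of this stands, and it limits the point to how events are classified in one set of counts.

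A reader might go further in four ways that the documents do not support.

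- *A third of the AE window disappears from the tolerability summary.* It does not, because the continuous summary covers it. What is absent is the related, severe or withdrawal count.
- *An AE that keeps a subject from the second dose goes unseen.* SAP 6.5.2 tabulates completion of each vaccination visit, and withdrawals with their reasons, by group. Protocol 8.1.3 requires withdrawal due to an AE to be distinguished from other causes. The case therefore rests mainly on related and severe nonserious AEs.
- *The regimen would look better tolerated than it is.* The category counts could be incomplete, but no rate is given for the gap. Both arms of this 1:1 placebo-controlled cohort use the same intervals. A bias between arms is not shown.
- *The closing rule declares the gap outside the protocol window.* Its parenthesis can equally be read as limiting the rule to AEs outside that window, which leaves the gap in. That reading also agrees with the continuous summary in the same section. The wording merits a clarification and no more.

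Immediate AEs are one of the listed categories, but they are defined by the first 30 minutes after vaccination and cannot fall in the gap.

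**Conclusion.** The point holds as a classification gap. In the Month-0, Month-2 Cohort, nonserious AEs starting from Visit 2 to the day before Vaccination 2 enter no related, severe or leading-to-withdrawal count, although the protocol collects them. The uncovered time is 19 to 38 days, about 31% of the window from Vaccination 1 to Visit 4 (range 21% to 40%).

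The size assumes that visits fall within their protocol windows and that the SAP's Stage 1 example defines the 1-month interval for this cohort too. It measures time, not events, and the fall from 0.80 to about 0.67 in the illustration depends on the assumed 5% rate and constant hazard. No data are lost, the cohort is exploratory and descriptive, and the Stage 1 primary endpoints are unaffected. The change is still worth making because it completes the category counts in the cohort that informs the dosing schedule, at almost no cost.

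**What to change.** 1. In SAP 3.1.4, add a fifth interval for the Month-0, Month-2 Cohort: "AEs from Vaccination 1 through 1 month after Vaccination 2". This is already an endpoint in Protocol 2 and SAP 3.3.
2. In the second paragraph of SAP 6.1.4.2, apply the related, severe and leading-to-withdrawal counts to that interval for this cohort, alongside the two 1-month intervals.
3. As a minor clarification, state that the closing rule on unsummarized events applies only to nonserious AEs outside each cohort's Protocol 8.1.4 collection window.

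The cost is a few lines of SAP text and one extra column or table for about 62 subjects. The data are already collected, and neither the protocol nor site procedures need to change.
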